5.11. Safety Analyses

[figure not shown]
The proposed intervention, use of a lipid-rich emollient, poses very little risk. For this reason, we defer to the DSMB to review safety information and recommend follow-up analysis. A priori safety analyses are specified elsewhere and included here for reference, but are not planned as part of the primary analysis.

The most plausible adverse events (AEs) are skin reactions to added ingredients in the study emollients, though we have intentionally selected simple formulations. Participants are asked to report any skin care product-related adverse event during quarterly contacts or communications with the clinical coordinating center. Research coordinators will record any skin care product-related AEs reported in the chart. We will provide the DSMB with annotated summaries of adverse events categorized by type and specific emollient, along with the denominator of dyads who selected the specific emollient. A dyad may be counted more than once if they select different emollients at different time points. Adverse reactions that affect >5% of dyads randomized to either arm will be reported.

Participants are asked to report any serious adverse events (SAEs) during quarterly contacts. The SAE most appropriate in this population include inpatient hospitalization or prolongation of hospitalization and a significant medical incident. AEs and SAEs are assessed to identify unanticipated problems. Unanticipated problems are unexpected, related to participation in the research, and places participants at a greater risk of harm than was previously known. We also record any deaths.

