10.4.4 Analysis of Key Secondary Endpoints

To test the hypothesis that emollient use delays onset of AD, we will compare time to onset using child's age in months with discrete time-to-event methods.⁸⁴ Time to AD onset will be defined in two ways, as (1) parental report of age of eczema onset and (2) age at first diagnosis recorded in patient chart. Censoring will occur at the date of last parental report or last visit recorded in the patient chart. We will also compare the intervention and control groups with respect to conditions and symptoms that include the need for topical therapy, asthma, food allergy symptoms, and dichotomized disease severity measures as binary measures, sleep loss days as counts, and AD severity scores (POEM and IDQOL) as continuous measures. We will test for differences using logistic, Poisson, or linear regression, adjusting for stratification variables. The incidence of adverse events at two years of age will also be compared between the treatment and control groups with a two-tailed chi-square test at the 0.05 level of significance.

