Table Title	Population	Time Point(s)	Endpoint	Endpoint Type	Summary Statistics by Treatment Assignment
Breathing Problems	ITT	12m,24m	Ever wheeze	Binary(Y/N)	p%(x/n)
			Number of wheeze events over past year (cat)	Count	p%(x/n)
			Wheeze without cold	Binary(Y/N)	p%(x/n)
			Diagnosed asthma	Binary(Y/N)	p%(x/n)
			Asthma predictive index-Y/N (derived)	Binary(Y/N)	p%(x/n)
Allergies	ITT	12m,24m	Skin Prick Test or Blood test	Binary(Y/N)	p%(x/n)
			Food allergy symptoms	Binary(Y/N)	p%(x/n)
			Food exposure	Binary(Y/N)	p%(x/n)
Severity of symptoms and influence on quality of life	AD population	12m,24m	POEM score (0-28)	Continuous	n, mean, SD, Median, min, max
			IDQOL score (0-30)	Continuous	n, mean, SD, Median, min, max
	ITT	12m,24m	Parent-rated health status	Ordinal(1-5)	p%(x/n) n, mean, SD, Median, min, max
			Days of disrupted sleep in the past week	Count(0-7)	p%(x/n) n, mean, SD, Median, min, max
			Adverse reaction to skin product	Binary(Y/N)	p%(x/n)
Adverse events	ITT	12m,24m	Type	Categorical	p%(x/n)
			Ended	Binary(Y/N)	p%(x/n)
			Severity	Categorical	p%(x/n)
			Require HCP visit	Binary(Y/N)	p%(x/n)
			Diagnosis	Categorical	p%(x/n)
			AE Treatment-Y/N	Binary(Y/N)	p%(x/n)
			AE Treatment-name	Categorical	p%(x/n)
			SAE listing	Narrative	n/a
					p%(x/n)
Contact info change	ITT	Any time			p%(x/n)

Table 5. Exploratory analyses

Subgroup	Intervention cumulative incidence	Usual care cumulative incidence	Difference (risk difference) 90% CI	Difference in differences	Risk Ratio 90% CI	Difference (ratio scale)	P value for interaction
Family history of atopy							
Yes							
No							
Climate							
Dry							
Wet							
Domestic animals							
Any							
None							
Cat(s)							
Dog(s)							
Farmanimal(s)							
Sex							
Female							
Male							
Age at randomization							
Youngest							
Middle							
Oldest							
Emollient type used							
CeraVe							
Others							
None							

6. References

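### The >5% reporting rule for adverse reactions in SAP 5.11 does not match SAP Table 4, and the SAP neither repeats nor cites the protocol's between-arm adverse-event test

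*SAP*

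**What the plan says.** **Protocol.** Section 10.2.2 lists the incidence of skin care-related adverse events, together with tolerability, among the key secondary endpoints, and refers the reader to the SAP for the full list. Section 10.4.4 says that adverse-event incidence at two years of age will be "compared between the treatment and control groups with a two-tailed chi-square test at the 0.05 level of significance".

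**SAP 5.11.** The section says "we defer to the DSMB to review safety information and recommend follow-up analysis". It then says: "A priori safety analyses are specified elsewhere and included here for reference, but are not planned as part of the primary analysis". It does not say where elsewhere is. For the board it promises: "We will provide the DSMB with annotated summaries of adverse events categorized by type and specific emollient". The denominator there is the dyads who selected that emollient, and a dyad that switches product may count more than once. The paragraph closes with the reporting rule: "Adverse reactions that affect >5% of dyads randomized to either arm will be reported". No comparison between arms is described.

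**SAP 5.12, Table 4.** The row "Adverse reaction to skin product" is a yes/no variable in the ITT population at 12 and 24 months, shown as a percentage with counts by treatment assignment. Further rows give type, severity, diagnosis and treatment, and there is a narrative listing of SAEs. No frequency threshold is attached, and no effect estimate, confidence interval or test is planned for these rows.

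**SAP 5.1 and 5.4.** The secondary endpoints include skin infections (in 5.1), but neither section contains a skin-product adverse-event endpoint.

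**The concern.** Two parts of one SAP give different rules for which skin reactions are reported, and an analyst has no basis for choosing between them. Following the text of 5.11 would satisfy the plan while leaving out a reaction several times more frequent with emollient than without. Following Table 4 would show the counts, but with nothing to say how large the excess is or how precisely it is known, although the protocol promised a test.

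This matters because the product is preventive and is given to infants without established eczema. Protocol 1.5.1 names irritant contact dermatitis, and more rarely allergic contact dermatitis, as the main risk. A reader weighing prevention against harm needs the excess risk of skin reactions by randomised arm. Summaries by chosen emollient do not supply it: their denominators are self-selected users, dyads can be counted twice, and controls do not select a study product.

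**Working it through.** **Inputs from the documents.** 625 dyads per arm, 1:1 (SAP 2.3); threshold above 5% of dyads randomised in either arm (SAP 5.11); Safety Population is all randomised participants (SAP 3.6); two-tailed chi-square at 0.05 (Protocol 10.4.4). The documents give no skin-reaction rates, so all counts and rates below are illustrative.

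**The plan's own figure.** The 625 comes from the primary sample size. Pooled-variance formula for two proportions, 24% vs 16.8%, two-sided 0.05, 80% power:

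n = [1.960·√(2 × 0.204 × 0.796) + 0.842·√(0.24 × 0.76 + 0.168 × 0.832)]² / 0.072² = 491 per arm, 982 in total.

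This reproduces SAP 2.3. Inflating for 20% loss, 982/0.80 = 1,228, close to the planned 1,250. No power is stated for any safety comparison.

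**Threshold in counts.** 0.05 × 625 = 31.25, so a reaction exceeds 5% only from 32 dyads in one arm. The largest count that stays below is 31 (4.96%).

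**An excess just below the threshold.** With 31 vs 10 events:

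- Risk difference = 31/625 − 10/625 = 0.0496 − 0.0160 = 0.0336, or 3.4 points; risk ratio 3.1.
- Pooled risk = 41/1,250 = 0.0328; z = 0.0336/√(2 × 0.0328 × 0.9672/625) = 3.33; chi-square = 11.1; p = 0.0009 (Fisher 0.0012).
- Wald 95% CI: 0.0336 ± 1.96·√[(0.0496 × 0.9504 + 0.016 × 0.984)/625] = 1.4 to 5.3 points.

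Other control counts against 31:

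| Control count | Risk ratio | Difference (points) | Pearson p | Fisher p |
|---|---|---|---|---|
| 6 | 5.2 | 4.0 | 0.00003 | 0.00003 |
| 10 | 3.1 | 3.4 | 0.0009 | 0.0012 |
| 16 | 1.9 | 2.4 | 0.026 | 0.036 |
| 17 | 1.8 | 2.2 | 0.039 | 0.055 |
| 18 | 1.7 | 2.1 | 0.058 | 0.079 |

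Pearson's test is significant for every control count up to 17. At 17 the result depends on which test is used.

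**How often this could happen.** Exact binomial sums with 625 per arm give the chance that an intervention excess is significant (pooled two-proportion test, two-sided 0.05) while neither arm exceeds 5%:

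| Assumed true rates, intervention vs control | Chance |
|---|---|
| 4% vs 1% | 85% |
| 3% vs 1% | 74% |
| 4.5% vs 1.5% | 64% |
| 4% vs 2% | 46% |
| 5% vs 2% | 38% |

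These take the rule as applied to one yes/no reaction variable. The sentence does not say whether it applies to any reaction or to each type. Applied by type, every type would need its own 32 dyads.

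**The case against.** Several stronger readings are tempting, and the documents do not support them.

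- **A reader might infer that rarer reactions are withheld.** SAP 5.11 does not say that only reactions above 5% are reported. The same paragraph gives the DSMB summaries with no frequency cut-off, Protocol 8.2 sends adverse events to the DSMB semi-annually and summaries to the IRB at least annually, and Table 4 would print the counts by arm. What can be missing is the reaction from the 5.11 report and any inference about it, not the raw numbers.
- **A reader might infer that the SAP dropped the protocol's test.** Section 5.11 says safety analyses are specified elsewhere, which could mean the protocol or the monitoring plan. Its remark that they "are not planned as part of the primary analysis" separates safety from the primary analysis and cancels nothing. The SAP revision history records no removal. The test is unmentioned, which is weaker than deleted. Section 5.11 also contains a figure that was not available for this review.
- **A reader might extend the threshold to SAEs.** The sentence concerns adverse reactions and sits in the paragraph on skin-product events. SAEs have their own paragraph without a threshold and a listing in Table 4.
- **A reader might say there is no control group.** That is true only of the by-emollient summaries. The 5% rule and Table 4 both refer to randomised arms.
- **A reader might quote 31 against 0.** No rate in the documents supports that. Controls may use emollients when dry skin develops, so some control reactions are to be expected.

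What remains is that the two SAP passages are unreconciled, that the cross-reference names no source, and that Table 4 alone does not deliver the comparison in Protocol 10.4.4.

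**Conclusion.** The point holds as an inconsistency with a practical consequence. SAP 5.11 and Table 4 give different reporting rules for skin-product reactions, and the SAP is silent on a between-arm comparison that the protocol specifies for what it calls a key secondary endpoint. At 625 per arm, an excess of about two- to five-fold can be statistically clear and still fall below the 5.11 threshold. At 31 vs 10 it is 3.4 points (95% CI 1.4 to 5.3), and Table 4 would show it only as untested counts.

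The 32-dyad threshold and the mismatch follow directly from the documents. The sizes and probabilities rest on assumed counts and rates and show what the rule permits, not what is expected. Suppression of safety data and deliberate removal of the test are not established.

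**What to change.** Before the dataset is locked, amend SAP 5.11 as follows:

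1. Remove the >5% threshold for skin-product reactions, or state that Table 4 governs what is reported.
2. Report all skin-product reactions by randomised arm in the Safety Population, with the risk difference, 95% CI and the protocol's two-sided test, using an exact test if counts are sparse. The interval goes beyond what Protocol 10.4.4 requires, but it is what a reader needs to judge the excess.
3. Cite Protocol 10.4.4 in place of the unspecified cross-reference, and add the skin-product adverse-event endpoint to SAP 5.1 and 5.4 so that they agree with Protocol 10.2.2.
4. Keep the by-emollient DSMB summaries and label them descriptive.

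SAE reporting needs no change. The cost is a few sentences of SAP wording and one small table. The data are already collected through the quarterly contacts and the chart review.

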5.12. Figures and tables

Figure 1: Screening flowchart (separate from CONSORT diagram, Figure 2)

Future questions related to CONSORT figure:

How to include withdrawn from certain activities? (partial withdrawal) Often reach out shortly after randomization b/c unable to fully comply but may be willing to complete questionnaires.

Also variable in how much emollient requested

Figure 2: CONSORT Flow Diagram

[figure not shown]

Figure 3: Follow-up in the randomized/intention-to-treat (ITT) population

Time point	Intervention/Control Responded	Intervention/Control Missed	Intervention/Control Withdrawn
1 (≤ 2 m)	n (%)	n (%)	n (%) of each: D/C, moved, lost
2 (3m)	n (%)	n (%)	n (%) of each: D/C, moved, lost
3 (6m)	n (%)	n (%)	n (%) of each: D/C, moved, lost
4 (9m)	n (%)	n (%)	n (%) of each: D/C, moved, lost
5 (12m)	n (%)	n (%)	n (%) of each: D/C, moved, lost
6 (15m)	n (%)	n (%)	n (%) of each: D/C, moved, lost
7 (18m)	n (%)	n (%)	n (%) of each: D/C, moved, lost
8 (21m)	n (%)	n (%)	n (%) of each: D/C, moved, lost
9 (24m)	n (%)	na	n (%) of each: D/C, moved, lost
Chart review	n(%)	na	n (%) not found, no consent

Time points 1, 5, 9 (gold): Long-form questionnaires; time points 2, 3, 4 and 6, 7, 8 (white): Brief follow-up.

m: months; n: count; %: percent of randomized total in arm; D/C: discontinued, confirmed by study personnel; moved: moved out of area; lost: lost to follow-up without being able to confirm a reason; na: not applicable.

Responded: full or partial response given; Missed: no response at given time point but later response exists; Withdrawn: No response at this or later time contacts (chart review may be complete). The sum of each row should equal the sum of (responded + missed) in the previous row.

Table 4: Planned summaries of study variables

Table Title	Population	Time Point(s)	Endpoint	Endpoint Type	Summary Statistics by Treatment Assignment
Disposition	ITT	Baseline to 24m each 3m	Disposition	Categorical (AD, no AD, lost to follow-up)	Count
Baseline Variables	ITT	Baseline	Age at enrollment	Weeks	n, mean, SD, Median, min, max
			Parental atopy	Binary(Y/N)	p%(x/n)
			Siblings with atopy	Binary(Y/N)	p%(x/n)
			Any parent or sibling with any atopy	Binary(Y/N)	p%(x/n)
			Home location	Categorical (urban, suburban, rural, etc.)	p%(x/n)
			Farm living	Binary(Y/N)	p%(x/n)
			Dog ownership	Binary(Y/N)	p%(x/n)
			Cat ownership	Binary(Y/N)	p%(x/n)
			Probiotic pills	Binary(Y/N)	p%(x/n)
			Dry skin	Binary(Y/N)	p%(x/n)
			Baths/week	Count (0-7+)	p%(x/n) n, mean, SD, Median, min, max
			Prior emollient use	Binary(Y/N)	p%(x/n)
			Prior emollient type	Categorical	p%(x/n)
			Prior emollient brand	Descriptive	p%(x/n)
Emollient Choices	Treatment Group	Baseline 24m or last refill	Prior emollient use per week	Count (0-7+)	p%(x/n) n, mean, SD, Median, min, max
			Gender	Binary(M/F)	p%(x/n)
			Ethnicity	Binary(Hispanic)	p%(x/n)
			Race	Categorical	p%(x/n)
			Education level	Categorical	p%(x/n)
			Emollient choice-baseline	Categorical	p%(x/n)
			Emollient choice-end of study	Categorical	p%(x/n)
			Switched from baseline	Binary(Y/N)	p%(x/n)

Table Title	Population	Time Point(s)	Endpoint	Endpoint Type	Summary Statistics by Treatment Assignment
Cumulative incidence of AD	ITT	24m	Primary outcome: Provider diagnosis of AD in patient chart	Binary(Y/N)	Relative risk(RR) for cumulative incidence
	ITT	12m,24m	Provider diagnosis of AD in patient chart at age 1 year and age 2 years	Binary(Y/N)	RR
	Complete case	12m,24m	Provider diagnosis of AD in patient chart (complete case)	Binary(Y/N)	RR
	ITT	12m,24m	Cumulative incidence of AD by parental report of provider diagnosis	Binary(Y/N)	RR
	ITT	12m,24m	Cumulative incidence of AD by parental report of Children's Eczema Questionnaire	Binary(Y/N)	RR
Age of onset of AD	ITT	All time points	Age of onset by chart review, parent report	Time to event	Kaplan-Meier
Skin Problems	ITT	12m,24m	Dry Skin	Binary(Y/N)	p%(x/n)
			Diagnosed eczema	Binary(Y/N)	p%(x/n)
			Red rash	Binary(Y/N)	p%(x/n)
			Itching	Binary(Y/N)	p%(x/n)
			Areas of rash	Categorical	p%(x/n)
Skin infections	ITT	12m,24m	Presence/absence at any time	Binary(Y/N)	p%(x/n)
			Type	Categorical	p%(x/n)
Rash treatment	AD population	12m,24m	Rash treatment Y/N	Binary(Y/N)	p%(x/n)
			Prescription treatment Y/N	Binary(Y/N)	p%(x/n)
			OTC treatment Y/N	Binary(Y/N)	p%(x/n)
			Specific type	Categorical	p%(x/n)
Skin care	ITT	12m,24m	Baths/week	Count(0-7)	p%(x/n) n, mean, SD, Median, min, max
			>2 baths/week	Binary(Y/N)	p%(x/n)
		12m,24m	>1 bath/week	Binary(Y/N)	p%(x/n)
		All time points before AD diagnosis, if applicable	Frequent emollient user: Report 3 or more days per week at majority of follow-up points	Binary(Y/N)	p%(x/n)
		Q3 months	Moisturizer use Y/N	Binary(Y/N)	p%(x/n)
			Emollient use days/week	Count(0-7)	n, mean, SD, Median, min, max
			Emollient type	Categorical	p%(x/n)
			Which emollients	Categorical	p%(x/n)

Table Title	Population	Time Point(s)	Endpoint	Endpoint Type	Summary Statistics by Treatment Assignment
Breathing Problems	ITT	12m,24m	Ever wheeze	Binary(Y/N)	p%(x/n)
			Number of wheeze events over past year (cat)	Count	p%(x/n)
			Wheeze without cold	Binary(Y/N)	p%(x/n)
			Diagnosed asthma	Binary(Y/N)	p%(x/n)
			Asthma predictive index-Y/N (derived)	Binary(Y/N)	p%(x/n)
Allergies	ITT	12m,24m	Skin Prick Test or Blood test	Binary(Y/N)	p%(x/n)
			Food allergy symptoms	Binary(Y/N)	p%(x/n)
			Food exposure	Binary(Y/N)	p%(x/n)
Severity of symptoms and influence on quality of life	AD population	12m,24m	POEM score (0-28)	Continuous	n, mean, SD, Median, min, max
			IDQOL score (0-30)	Continuous	n, mean, SD, Median, min, max
	ITT	12m,24m	Parent-rated health status	Ordinal(1-5)	p%(x/n) n, mean, SD, Median, min, max
			Days of disrupted sleep in the past week	Count(0-7)	p%(x/n) n, mean, SD, Median, min, max
			Adverse reaction to skin product	Binary(Y/N)	p%(x/n)
Adverse events	ITT	12m,24m	Type	Categorical	p%(x/n)
			Ended	Binary(Y/N)	p%(x/n)
			Severity	Categorical	p%(x/n)
			Require HCP visit	Binary(Y/N)	p%(x/n)
			Diagnosis	Categorical	p%(x/n)
			AE Treatment-Y/N	Binary(Y/N)	p%(x/n)
			AE Treatment-name	Categorical	p%(x/n)
			SAE listing	Narrative	n/a
					p%(x/n)
Contact info change	ITT	Any time			p%(x/n)

Table 5. Exploratory analyses

Subgroup	Intervention cumulative incidence	Usual care cumulative incidence	Difference (risk difference) 90% CI	Difference in differences	Risk Ratio 90% CI	Difference (ratio scale)	P value for interaction
Family history of atopy							
Yes							
No							
Climate							
Dry							
Wet							
Domestic animals							
Any							
None							
Cat(s)							
Dog(s)							
Farmanimal(s)							
Sex							
Female							
Male							
Age at randomization							
Youngest							
Middle							
Oldest							
Emollient type used							
CeraVe							
Others							
None							

6. References

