6.3 Final Study Contact

Contact 10, Infant Age 24 Months + 90 days

Infant health record review by blinded research coordinator to record clinical assessments through 2-year well-child check (up to 27 months of age). Coordinator to collect the following:

- Primary Endpoint: Provider diagnosis of AD or eczema
 - Any diagnosis of eczema, atopic dermatitis, or atopic eczema at any visit
 - Any qualifiers like “probable” or “probable.” These will be coded as having atopic dermatitis for the primary analyses.
 - Date of first diagnosis
 - Treatment(s) used for AD- dose, frequency
- Secondary Endpoints from chart review
 - Date of first diagnosis of AD by clinician in chart
 - Approximate date of onset of symptoms if recorded (age of child in months)
 - Presence of wheeze and date of onset
 - Diagnosis of atopic comorbidities: asthma, allergic rhinitis, food allergy
 - Any allergy testing- skin prick tests or blood
- Medication history: Any skin-directed prescription therapies:
 - Antibacterial (e.g. mupirocin, bacitracin)
 - Anti-inflammatory (topical corticosteroids, topical calcineurin inhibitors, crisaborole)
 - Antifungals (e.g. ketoconazole, econazole, terbinafine)
 - Antivirals (e.g. acyclovir ointment)
 - Any oral antibiotics prescribed for any indication- name of antibiotic, duration indicated on prescription, and indication if stated
- Provider diagnosis of hay fever/allergies, asthma, and/or food allergies
- Gestational age
- Birth weight
- Adverse events
 - Only skin product-related adverse events mentioned in the clinical chart will be captured. Event start and stop dates (if known) will be recorded, outcome and treatments needed.
 - Any serious adverse events (SAEs), not only skin-related, will be captured

- In infants who were diagnosed with AD/eczema:
 - Date of diagnosis
 - Severity
 - Prescribed medications for treatment of AD, eczema, or rash

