8 ADVERSE EVENTS REPORTING

Adverse events (AEs) in this study will be identified (1) by parent report through responses the parent provides in electronic contacts (refer to section 5.4), selecting the link for reporting skin product-related AEs provided on the websites, (2) by parent report via phone or email contact to the CCC, and (3) by review of the infants' medical record through ages 27 months. AEs will be graded as to their expectedness and attribution by the principal investigator (unrelated, possibly, probably or definitely related to the protocol). Due to the nature and low risk of the intervention, only skin product-related adverse events in randomized infants will be actively captured by patient report at least quarterly. These skin product-related AEs may qualify as serious adverse events (SAEs) or Unanticipated Problems (UPs) and will be actively monitored and reported by the PI and study team on a daily basis. All SAEs, not just skin product-related, will also be captured by patient report quarterly.

Clinic chart audits through 27 months will record all skin product-related AEs and UPs and all SAEs (whether or not they are skin product-related) and will be reported according to the timelines specified in the MOOP and the DSMP.

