8.1 Definitions

8.1.1 *Adverse Event (AE)*

Any untoward or undesirable, although not necessarily unexpected, event experienced by a human participant that may be a result of:

- The interventions and interactions in the research
- The collection of identifiable private information in the research
- An underlying disease, disorder, or condition of the participant that could be reasonably attributed to emollient use
- Other circumstances unrelated to the research or any underlying disease, disorder, or condition of the participant

8.1.2 *Serious Adverse Event (SAE)*

Any AE that:

- Is fatal
- Is life-threatening
- Is persistent or significantly disabling or incapacitating
- Results in inpatient hospitalization or prolongation of hospitalization
- Results in psychological or emotional harm requiring treatment (not applicable in our population)
- Creates a persistent or significant disability
- Causes a congenital anomaly or birth defect (not applicable in our population)
- Results in a significant medical incident (considered to be a serious study related event because, based upon appropriate medical judgment, it may jeopardize the participant and may require medical or surgical intervention to prevent one of the outcomes listed in this definition)

8.1.3 *Unanticipated Problem (UP)*

Events that are not expected given the nature of the research procedures and the participant population being studied and suggest that the research places participants or others at a greater risk of harm or discomfort related to the research than was previously known or recognized. Harm to a participant need not occur for an event to be an unanticipated problem.

8.1.4 *Deviation*

A deviation is any noncompliance with the clinical study protocol, Good Clinical Practice, or Manual of Operating Procedures requirements. The noncompliance may be on the part of the participant, the investigator, or study staff. As a result of deviations, corrective actions are to be developed by the study staff and implemented promptly.

All deviations will be reported according to the timelines specified in the MOOP and the DSMP.

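### All-cause SAEs are collected in both arms, but the SAP plans only a narrative listing and neither carries forward nor defines for SAEs the protocol's between-arm adverse event comparison

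*SAP*

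**What the plan says.** **Collection.** Protocol section 8 restricts non-serious events: "only skin product-related adverse events in randomized infants will be actively captured by patient report at least quarterly". SAEs have no such restriction: "All SAEs, not just skin product-related, will also be captured by patient report quarterly". Section 6.3 repeats this for the final chart review by a blinded coordinator, which runs to 27 months: "Any serious adverse events (SAEs), not only skin-related, will be captured". The SAE definition in section 8.1 starts from any AE and includes an event that "Results in inpatient hospitalization or prolongation of hospitalization".

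**Analysis in the protocol.** Section 10.4.4 states: "The incidence of adverse events at two years of age will also be compared between the treatment and control groups". The test is a two-tailed chi-square at 0.05. SAEs are not named.

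**Analysis in the SAP.** The last column of Table 4 (section 5.12) gives summary statistics by treatment assignment. Most adverse event rows carry a proportion, for example "Require HCP visit Binary(Y/N) p%(x/n" (the closing bracket is cut off). The SAE row reads "SAE listing Narrative n/a". Section 5.11 describes reporting ("Participants are asked to report any serious adverse events (SAEs) during quarterly contacts") and leaves safety review and follow-up analysis to the DSMB. It says that a priori safety analyses are specified in another place, and it contains no count or contrast of SAEs by arm. Section 3.6 defines a Safety Population of all randomised participants, but the adverse event rows in Table 4 use the ITT population.

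**The concern.** Parents know their arm, and only one arm is sent emollient. Whether a rash is reported as product-related can depend on that knowledge. SAEs enter the database without anyone having to blame a product, so they are the adverse event class least exposed to attribution and the natural basis for a between-arm safety comparison. The SAP gives this class the weakest planned output.

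The trial tests daily full-body emollient in infants not selected for risk, and its result could inform advice to that population. Readers will want to know how many infants in each arm had a serious event and how precisely any difference is estimated. A set of narratives gives neither an excess with its uncertainty nor a reassuring upper limit.

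**Working it through.** **1. Where each event class is analysed.**

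| Event class | Attribution needed? | By-arm output named |
|---|---|---|
| Skin-product reactions | Yes | Proportions in SAP Table 4; within the protocol 10.4.4 chi-square |
| Skin infection | No | Secondary outcome in SAP 5.1 (item 5: parent report, chart diagnosis, chart topical antibiotics), two-sided tests, proportions in Table 4 |
| All-cause SAEs, hospitalisation, serious non-skin infection | No | None by name; within 10.4.4 only because an SAE is an AE |

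The third row is the gap. Read literally, 10.4.4 counts an infant with a product-related rash and an infant admitted to hospital as the same event, and yields a p-value without an effect size.

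**2. What a by-arm estimate would offer.** The documents state no SAE rate or SAE precision, so there is no SAE figure to reproduce. As a check on the power formula, 24% versus 16.8% with 491 per arm gives 80.0%, which matches the plan's sample size for the primary outcome.

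Inputs: n = 625 per arm (protocol 10.3.2, SAP 2.3), two-sided 0.05. Control SAE risks p0 of 2% to 10% over follow-up are my assumption.

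- Risk difference half-width at equal risks: 1.96 × √(2·p0(1−p0)/n).
- Power = Φ[(|p1−p0| − 1.96·√(2·p̄(1−p̄)/n)) / √((p0(1−p0)+p1(1−p1))/n)], where p̄ is the mean of p0 and p1.
- SE(log RR) = √((1−p0)/(n·p0) + (1−p1)/(n·p1)).

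Example, 3% versus 6%: (0.03 − 1.96 × 0.01173)/0.01170 = 0.60, so power is 73%. SE(log RR) = √(0.97/18.75 + 0.94/37.5) = 0.277, so the 95% interval for RR 2.0 is 1.16 to 3.44.

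| Assumed control risk | Expected infants with an SAE per arm | Half-width (points) | Power, RR 2.0 | Power, RR 1.5 | Power, RR 2.0, 500 per arm |
|---|---|---|---|---|---|
| 2% | 12.5 | 1.55 | 54% | 20% | 46% |
| 3% | 18.75 | 1.89 | 73% | 29% | 63% |
| 5% | 31.25 | 2.42 | 92% | 45% | 85% |
| 10% | 62.5 | 3.33 | >99% | 76% | 99% |

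The last column allows for 20% loss (625 × 0.8 = 500).

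**3. What pooling would do.** Suppose skin-product events occur at rate a in both arms, independently of SAEs. The pooled risk is 1 − (1−a)(1−p). For SAE risks of 3% versus 6% and a = 2%, this is 4.94% versus 7.88%, so a risk ratio of 2.0 appears as 1.60. Power falls from 73% to 64% at a = 1%, 56% at 2%, 41% at 5%, 28% at 10% and 17% at 20%. The documents give no value for a. The SAP expects very little risk from the intervention, so the mild end may be the relevant one.

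**The case against.** A reader might infer that SAEs will never be compared between arms, and that an excess of serious infections on emollient would go unestimated. The documents do not support that, for four reasons.

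- Protocol 10.4.4 compares adverse events between arms, and under section 8.1 an SAE is an AE. On a plain reading SAEs fall within that test. What stands is that the test is not specific to SAEs, gives no estimate or interval, and is absent from the SAP.
- Skin infection, the theoretical harm named in protocol 1.5.1, is already compared by arm as a secondary outcome. What stands is that this comparison does not grade seriousness and does not reach hospitalisation or serious infection elsewhere. The documents name no specific concern about those events.
- SAP 5.11 refers to safety analyses specified in another place. Those documents were not supplied, so a by-arm SAE table may be planned there. What stands is that neither the protocol nor the SAP shows one, and interim review by the DSMB does not replace a pre-specified estimate in the final report.
- In the text as read from the PDF, an unlabelled `p%(x/n)` follows the SAE row. It may belong to a lost row or to the next block, and its owner cannot be determined. The SAE row itself reads n/a.

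Two further points against the concern are fair. The power figures depend wholly on assumed rates, and for a descriptive estimate power is not the main criterion. Capture is also imperfect: protocol 8.2 limits reporting to SAEs that reach the study team, and section 4.5 accepts that a chart may reveal the arm.

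**Conclusion.** The concern holds in a limited form. The SAP gives all-cause SAEs a narrative listing with no by-arm statistic, and it neither carries forward nor defines for SAEs the comparison in protocol 10.4.4. The missing output is a by-arm count and effect estimate for all-cause SAEs, hospitalisation and serious non-skin infection. The claim that nothing about serious harm would be compared goes too far.

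The size of the loss cannot be fixed from the documents. Across assumed control risks of 2% to 10%, an estimate from 625 per arm ranges from imprecise to informative for a doubling. For a 50% increase, power is only 20% to 45% at control risks of 2% to 5%. The dilution figures depend also on an assumed skin-event rate that is equal in both arms. The primary outcome and its inference are unaffected. This is a safety-reporting weakness that can be corrected cheaply and is worth correcting.

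**What to change.** In SAP Table 4 and section 5.11, replace the narrative-only entry with the number and percentage of infants with at least one SAE, by randomised arm, in the Safety Population. Show this overall, for hospitalisation and for infection-related SAEs, each with risk difference, risk ratio and 95% confidence interval, labelled descriptive. Count each infant once across parent report and chart audit, show the chart-audit-only result beside it because that source is blinded by design, and keep the narratives as a supplement.

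Reconcile this with protocol 10.4.4 by stating in the SAP that its comparison is run separately for skin-product adverse events and for SAEs. If the analyses specified in another place already contain such a table, cite that document and bring the table into the SAP.

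The cost is SAP wording, one additional table from data already entered in REDCap, and two short rules set before unblinding: how to match the same event across sources, and how to classify an SAE as infection-related. If SAEs prove rare the intervals will be wide, which is a reason for the descriptive label. No change to data collection or to the conduct of the trial is needed.
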